## **5. Subject Disposition**

### **5.1. Disposition**

A table will show the disposition of subjects with the number and percentage of subjects for the following categories:

- Subjects who entered OLE
- Subjects who completed the treatment in OLE
- Subjects who discontinued the treatment in OLE
- Subjects who completed the study
- Subjects who discontinued from the study

The reasons for study discontinuation will also be summarized.

Subject disposition data will also be presented in a listing.

### **5.2. Protocol Deviations**

Protocol deviations will be summarized by deviation type. A listing of all protocol deviations will be provided as well. A separate presentation will be provided for significant deviations during the OLE period only.

## **6. Demographics and Baseline Characteristics**

### **6.1. Demographics**

A summary of demographics and baseline characteristics will be presented for subjects who entered the OLE. The demographic characteristics will consist of age (years), sex, race, and ethnicity. The baseline characteristics will consist of baseline height (cm), baseline weight (kg), baseline body mass index (BMI) (kg/m^2), and hand dominance (left or right). Body mass index is calculated as (body weight in kilograms) / (height in meters). Age, baseline height, baseline weight, and baseline BMI will be summarized using descriptive statistics. The number and percentage of subjects by sex (Male, Female), race (White, African American, Asian, American Indian or Alaska Native, Native Hawaiian or Other Pacific

Islander, and Other), ethnicity (Hispanic or Latino, Not Hispanic or Latino) and hand dominance will also be reported.

Subject demographic and baseline characteristics will also be presented in a listing.

## 6.2. Baseline Disease Characteristics

Baseline disease characteristics include the following parameters:

- FSHD repeat number (1, 2, 3, 4, 5, 6, 7, 8, and 9)
- FSHD repeat category (1 to 3 repeats, 4 to 9 repeats)
- Clinical severity score (RICCI score 2, 2.5, 3, 3.5, 4)
- FSHD history
  - Age of symptom (years)
  - First symptom
    - Weakness
    - Difficulty smiling
    - Reaching over head
    - Walking
    - Running
    - Keeping up with peers
    - Pain
    - Others
  - Age at diagnosis (years)
  - Pain related to FSHD

Baseline disease characteristics will also be presented in a listing.

## 7. Treatments and Medications

### 7.1. Concomitant Medications

All medications used within 28 days prior to the date of screening through safety follow-up will be collected on the CRF (case report form). All medications will be coded according to the World Health Organization Drug Dictionary (WHODD Global B3 Mar 2019 or higher). A concomitant medication is defined as any medication that is taken on or after the date of study drug administration regardless when the medication is started up to 7 days after the last dose date.

For the purpose of inclusion in concomitant medication tables, incomplete medication start and stop dates will be imputed as follows:

Missing start dates (where UK, UKN, and UNKN indicate unknown or missing day, month, and year, respectively):

- UK-MMM-YYYY: If the month and year are different from the month and year of administration of study drug, assume 01-MMM-YYYY. If the month and year are the same as the administration of study drug month and year and the end date (after any imputation) is on or after the administration of study drug, then assume the first day of the month of the administration of study drug. If the month and year are the same as month and year of the study drug administration and the end date (after any imputation) is prior to the study drug administration, then assume the first day of the month of the administration of the study drug for the start date;
- DD-UKN-YYYY/UK-UKN-YYYY: If the year is different from the year of the study drug administration, assume DD-JAN-YYYY/01-JAN-YYYY of the collected year. If the year is the same as study drug administration year and the end date (after any imputation) is on or after the study drug administration, then assume the date of the study drug administration. If the year is the same as the study drug administration and the end date (after any imputation) is prior to the first dose of study drug, then assume the first day of the month of the administration of the study drug for the start date.

Missing stop dates (where UK, UKN, and UNKN indicated unknown or missing day, month, and year, respectively):

- UK-MMM-YYYY: Assume the last day of the month;
- DD-UKN-YYYY: Assume DD-DEC-YYYY;
- UK-UKN-YYYY: Assume 31-DEC-YYYY.

If the start date is completely missing and end date is not prior to the study drug administration, then the medication will be classified as concomitant. If the start date is completely missing and the end date is within 30 days prior to the first dose of study drug, then the medication will be classified as prior. If the end date is missing, then the medication will be classified as ongoing. Medications for which the start and end dates are missing will be classified as concomitant.

Concomitant medications will be summarized by Anatomical Therapeutic Chemical (ATC) classification level 4 and preferred term (PT), respectively. When ATC classification level 4 is missing, the next available ATC level will be used as ATC level 4.

The total number of concomitant medications and the number and percentage of subjects with at least one concomitant medication throughout the duration of the study will be presented. A separate presentation will be done for concomitant medications taken during the placebo-controlled treatment period and OLE. The number and percentage of subjects taking each concomitant medication will be summarized by sequence of actual treatment received in combination with entry point of OLE and overall.

Data on concomitant medications will also be presented in a listing.

## 7.2. Study Treatments

### 7.2.1. Extent of Exposure

The duration of exposure to losmapimod is the total number of days a subject is exposed to losmapimod; this duration is the interval from the first dose date of losmapimod to last dose date of losmapimod (ie, calculated as the date of last dose of losmapimod minus the date of first dose of losmapimod + 1). If the last dose date of losmapimod is missing, or if a subject is lost to follow-up, but the drug accountability log confirms that the subject has taken losmapimod, the visit date following the last completed drug accountability log will be used.

The exposure to losmapimod will also be characterized by cumulative dose, which is defined as the cumulative number of losmapimod tablets taken in the placebo-controlled treatment period and OLE.

The duration of exposure to losmapimod will be summarized for all subjects who entered OLE using summary statistics according to the sequence of actual treatment received in combination with entry point of OLE. For the Placebo BID/Losmapimod 15 mg BID column, only the duration of exposure while on losmapimod will be summarized. The duration of exposure will then be classified into the following categories: < 8 weeks, >= 8 weeks, >= 16 weeks, >= 24 weeks, >=36 weeks, >=48 weeks, >=60 weeks, >=72 weeks, >=84 weeks, >=96 weeks, >=108 weeks, >=120 weeks, >=132 weeks, >=144 weeks, >=156 weeks, >=168 weeks, >=180 weeks, >=192 weeks, >=204 weeks, and >=216 weeks and will be presented as the number and percentage of subjects in each duration category.

The total cumulative dose for losmapimod in mg will be defined as the total number of losmapimod tablets taken across all study days times 7.5 mg if 2 tablets were given while times 15 mg if 1 tablet was given. Average daily dose of losmapimod will be defined as cumulative dose of losmapimod divided by total days on losmapimod. The average daily dose and cumulative dose will be summarized using summary statistics according to the sequence of actual treatment received in combination with entry point of OLE. For the Placebo BID/Losmapimod 15 mg BID columns, only the cumulative dose and average daily dose for losmapimod will be summarized.

A summary of each subject's exposure to losmapimod will also be presented in a listing.

### 7.2.2. Treatment Compliance

Losmapimod compliance will be calculated for each subject by taking into account whether a subject took all doses of losmapimod as instructed. The number of tablets taken will be calculated by subtracting the number of tablets returned from the number of tablets dispensed. The dosage taken will be calculated by summing the number of tablets taken times the corresponding tablet dosage.

The losmapimod compliance (%) for each visit will be calculated by dividing the total number of tablets taken up to the next visit by the total number of tablets prescribed at each visit and then multiplying by 100. Compliance (%) = [sum of ((total number of tablets dispensed – total number of tablets returned) \* corresponding tablet dosage [mg]) / (number of days in visit interval \* dosage [mg] prescribed per day)] \* 100. The overall losmapimod compliance (%) will be calculated by dividing the total dosages [mg] taken at all visits by the total dosages [mg] prescribed for all visits and then multiplying by 100.

The overall losmapimod compliance will be summarized by sequence of actual treatment received in combination with entry point of OLE. For the Placebo BID/Losmapimod 15 mg BID columns, only the treatment compliance for losmapimod will be summarized.

The number and percentage of subjects in different percentage compliance categories (<80%, >=80% to <120%, and >= 120% compliant) will be presented.

## 8. Efficacy Analysis

Efficacy endpoints will be summarized over time showing both the placebo-controlled treatment period and OLE data.

### 8.1. MSK MRI Muscle Fat Fraction, Lean Muscle Volume and Muscle Fat Infiltration

Measurement of the extent of skeletal muscle tissue replacement by fat in FSHD patients will be done through automatic skeletal muscle segmentation for the 3D muscle volumes and fat fraction analysis via robust algorithms using Dixon imaging. Schedule of MRI assessments are described in [Appendix 14.2](#).

**A. Longitudinal composite measures:** Longitudinal whole-body composite variables, incorporating pre-selected muscles, will be derived for longitudinal analysis of muscle fat fraction, lean muscle volume and muscle fat infiltration ( $MFF_{tot}$ ,  $LMV_{tot}$ , and  $MFI_{tot}$  respectively), as described in [Appendix 14.1](#). The scores will be derived by scientists at the MRI Service Provider (AMRA Medical Inc.).

The longitudinal composite observations of relative change in  $LMV$  is sensitive to low overall  $LMV$ . Therefore, a criterion is required for exclusion of such observations. To ensure that the relative change in  $LMV$  is reliable,  $LMV_{ref}$  ( $LMV$  at reference timepoint) needs to fulfill one of the below:

- Be at least 25 cl and consist of measurements from at least 2 muscles combined.
- Be at least 50 cl with measurements from at least one muscle.

Further, if the subject's individual muscles fulfill neither criteria, the change from reference timepoint in longitudinal composite scores for  $LMV$  (L),  $LMV$  (%),  $MFF$  (%), and  $MFI$  (%) are set to missing. If the individual muscles could fulfill at least one of the two bullets above, the change from reference time point in longitudinal composite scores for  $LMV$  (L),  $LMV$  (%),  $MFF$  (%), and  $MFI$  (%) are not set to missing.

For each treatment sequence/entry point of OLE, descriptive statistics of  $MFF_{tot}$ ,  $LMV_{tot}$ , and  $MFI_{tot}$  per visit as well as changes from baseline will be presented.

To assess the efficacy of losmapimod in the placebo group after rollover into the OLE and the durability of efficacy in the losmapimod group, the mean change from baseline (+- SE) by visit of  $MFF_{tot}$ ,  $LMV_{tot}$ , and  $MFI_{tot}$  will be graphically presented over both the placebo-controlled treatment period and OLE.

Three types of % change/year in longitudinal composite scores will be estimated:

- (1) % change/year for losmapimod using data from both the placebo-controlled treatment period and OLE

Data while the subject is on losmapimod will be considered in the analysis. For subjects who were randomized to losmapimod at baseline, data from both the placebo-controlled treatment period and OLE will be included in the analysis. For subjects who were randomized to placebo and transitioned to losmapimod at OLE, their data under losmapimod are considered in the analysis. A linear mixed-effects model will be used to analyze the longitudinal composite scores for each treatment sequence, with intercept and time as random effects, and with adjustment for repeat number category and region (EU, USA, and Canada). An unstructured covariance matrix will be used to model the correlations between repeated measurements within each subject. In addition, the % change/year will be presented and will be derived as  $[(\text{slope}/\text{baseline}) * (365/T) * 100]$  where baseline is the LS mean of the intercept and T is the duration of treatment with losmapimod minus 1.

- (2) % change/year for the losmapimod group and placebo group using data from the placebo-controlled treatment period for subjects who completed 48 weeks of treatment in the placebo-controlled treatment period

A linear mixed-effects model will be used to analyze the longitudinal composite scores, with treatment sequence as a fixed effect, and intercept, time and treatment sequence-by-time interaction as random effects, adjusting for repeat number category and region (EU, USA, and Canada). An unstructured covariance matrix will be used to model the correlations between repeated measurements within each subject. Within-treatment sequence LS mean of slope and the associated SE, intercept and the associated SE, difference in the LS mean of slope and the associated 2-sided 95% CI and 2-sided p-value will be derived from the linear mixed-effects model and will be provided in the summary table. In addition, the % change/year will be presented. It will be derived as  $[(\text{slope}/\text{baseline}) * (365/T) * 100]$  where baseline is the LS mean of the intercept and T is the duration of treatment with study drug minus 1. Difference in % change/year between treatment sequences will also be presented.

- (3) % change/year for each treatment sequence using data from the OLE for subjects who completed 48 weeks of treatment in the placebo-controlled treatment period

The same approach as in (2) will be used to analyze the longitudinal composite scores in the OLE.

In estimating the three types of % change/year, if any model using an unstructured covariance matrix does not converge, an AR(1) covariance structure will be used

instead. If either unstructured or AR(1) covariance matrix does not lead to a convergent model, a compound symmetric covariance structure will be used instead.

The purpose of estimating % change/year for each treatment sequence in (2) and (3) above is to explore the possibility that earlier treatment with losmapimod is better than delayed treatment and that the placebo group's progression slows after treatment with losmapimod.

The change from baseline in the composite parameters will also be summarized by subgroups identified in [Section 4.7](#) to evaluate consistency of treatment effects across the subgroups.

- B. **Individual Muscles:** For each muscle location, a similar method will be used to analyze muscle fat fraction (%), lean muscle volume (L), and muscle fat infiltration (%) per visit as well as changes from baseline.
- C. **Cross-sectional composite measures:** The cross-sectional composite scores will be used to correlate the results with Clinical Outcome Assessments (i.e., TUG, FSHD TUG and RWS). The convention that will be used to get extremity equivalent of the cross-sectional results is provided in [Table 8-1](#).

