## 1. Introduction

This statistical analysis plan (SAP) describes the analyses and data presentation for the Open-label extension (OLE) part of protocol FIS-002-2019 which is being conducted under the sponsorship of Fulcrum Therapeutics (Fulcrum) in accordance with applicable standard operating procedures. The efficacy analyses will be conducted at OLE visits with available subject data. Statistical analyses are being conducted under contract with █, part of Thermo Fisher Scientific, in collaboration with Fulcrum.

The Clinical, Data Management, and Biostatistics departments at █ will work diligently and collaboratively with Fulcrum to ensure that the data collected and analyzed for this study are of high quality. This will be accomplished in part by having thorough edit checks written, programmed, and updated as needed.

This SAP is based on the protocols version 4.0 (COVID-19 Pandemic Emergency Amendment) dated 10Apr2020 and version 5.0 dated 16Aug2022. This SAP contains definitions of analysis population, derived variables, and statistical methods for the analysis of the OLE and in some parts of this SAP, a combination of placebo-controlled treatment period and OLE analysis. A separate SAP was created for the placebo-controlled treatment period.

The OLE will evaluate the safety, tolerability, and efficacy of long-term dosing with losmapimod in treating subjects with Facioscapulohumeral Muscular Dystrophy type 1 (FSHD1).

The term study drug that is being used throughout this document refers to losmapimod and/or placebo.

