### **3. Investigational Plan**

#### **3.1. Overall Study Design and Plan**

Once subjects reach Week 48, they will have the option to roll over into the OLE, with all subjects receiving 15 mg PO losmapimod tablets BID. Subjects who wish to roll over into the OLE must complete all procedures from the Week 48 end of placebo-controlled treatment period/start of OLE visit.

Subjects will remain in the OLE until study drug approval or until the study is discontinued by the sponsor. All subjects who complete or discontinue from treatment will complete a safety follow-up visit 7 days (+/- 3 days) after the last dose of study drug.

During the OLE, subjects will attend clinic visits approximately every 12 weeks. Study drug (open-label losmapimod) will be administered BID and should be taken with food. The first dose of OLE drug will be the day after the Week 48 visit.

The OLE will evaluate the safety and tolerability of long-term dosing with losmapimod in treating subjects with FSHD1. The efficacy data will be collected until protocol version 5.0 is executed. The efficacy analysis will be conducted when available efficacy data are fully cleaned.

Prior to the COVID-19 pandemic, subjects who reached the Week 24 visit had the option to roll over into the OLE. Subjects who had already rolled over to the OLE prior to the COVID-19 pandemic will remain on open label treatment. Their next clinic visits will follow the assessments for the Week 36 and Week 48 visits in the placebo-controlled portion of the study as described in the COVID-19 Pandemic Emergency protocol version 4.0. The first dose of OLE drug for these subjects will be the day after the Week 24 visit.

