#### **4.4. Baseline, Study Day, and Change from Baseline Definitions**

Unless indicated otherwise, baseline will be defined as the last non-missing evaluation on or before the day of first dose of study drug in the placebo-controlled treatment period. If the last non-missing evaluation and the study drug administration occur on the same day, timing of the evaluation will be used to determine the pre- or post-dose. If timing is not available, the evaluation is considered pre- or post-dose based on the schedule of events for that assessment. For example, AEs and concomitant medication are considered post-baseline evaluations.

For the OLE baseline, it is defined as the last non-missing evaluation before the first dose of losmapimod in the OLE.

Relative study days will be calculated as:

$(\text{assessment date} - \text{first study drug administration date}) + 1$

if the assessment date is on the same day or after the first dosing date, otherwise:

$(\text{assessment date} - \text{first study drug administration date})$ .

Where applicable, study day relative to first dose of losmapimod will also be provided and this will be calculated as:

$(\text{assessment date} - \text{first losmapimod administration date}) + 1$

if the assessment date is on the same day or after the first dosing date, otherwise:

$(\text{assessment date} - \text{first losmapimod administration date})$ .

Both study days will be presented on all listings where appropriate.

Change from baseline will be computed as (post-baseline assessment value - baseline assessment value). Percent change from baseline will be computed as  $(\text{change from baseline value} / \text{baseline assessment value}) * 100$ . For the OLE visits, change from baseline will be computed based on both baseline assessment value, baseline in the placebo-controlled treatment period and baseline in OLE.

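### SAP 8.1 annualizes a mixed-model slope with 365/T, which is right only if time is coded as a fraction of T; otherwise % change/year falls as 1/T

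*SAP*

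**What the plan says.** Section 8.1 of the SAP plans three annualized rates for the MRI longitudinal composite scores, each from a linear mixed model with time among its random effects.

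- Analysis (1) uses all data on losmapimod. The rate is (slope/baseline) × (365/T) × 100, "where baseline is the LS mean of the intercept and T is the duration of treatment with losmapimod minus 1".
- Analysis (2) uses the placebo-controlled period. The formula is the same, "where baseline is the LS mean of the intercept and T is the duration of treatment with study drug minus 1". A difference in % change/year between sequences is also planned.
- Analysis (3) uses the open-label extension (OLE): "The same approach as in (2) will be used to analyze the longitudinal composite scores in the OLE".

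The stated aim of (2) and (3) includes exploring whether the placebo group's "progression slows after treatment with losmapimod".

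Four other places bear on T and on time:

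- Section 7.2.1 counts losmapimod exposure in days, "calculated as the date of last dose of losmapimod minus the date of first dose of losmapimod + 1".
- Section 1: "The term study drug that is being used throughout this document refers to losmapimod and/or placebo".
- Section 4.4 defines study day from first dose and adds: "Where applicable, study day relative to first dose of losmapimod will also be provided". Table 4-1 maps study days to nominal weeks.
- Section 3.1: "The efficacy data will be collected until protocol version 5.0 is executed". Dosing continues after that.

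No section gives the unit of time in the model or says that time is divided by T. Sections 8.2.1 to 8.2.3 reuse the approach for reachable workspace, classic TUG and dynamometry. Section 8.1 applies a similar method to individual muscles.

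**The concern.** The factor 365/T annualizes a total change accumulated over T days. A model slope is a change per unit of time, so multiplying it by 365/T divides by elapsed time a second time. With a fixed time unit the reported figure then depends on how long the group was treated as well as on how fast it changed.

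The artefact runs in the direction the trial hopes to see. Longer treatment gives a smaller apparent rate, so early starters look slower than delayed starters in (1), and the extension looks slower than the placebo-controlled period when (3) is set beside (2).

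T itself is left open in three respects:

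- The slope and intercept are group-level, but the SAP does not say whether T is a subject, group or nominal value.
- In (3), T is time on study drug, a term that covers placebo too, so its starting point is not fixed.
- A T taken to last dose keeps growing after the last efficacy measurement.

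**Working it through.** The documents give no numerical % change/year, so there is no plan figure to reproduce. The check is one of units, followed by illustrative values.

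**Inputs**

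- T in days = duration minus 1 = last dose date minus first dose date (SAP 7.2.1 and 8.1).
- Illustrative T = 7 × weeks − 1, following the scheduled days in SAP Table 4-1: Week 48 is day 336, Week 96 is 672, Week 144 is 1008 and Week 216 is 1512.
- Assumption: a true linear rate of -2% of baseline per year in every group and period. The ratios below do not depend on this value.

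**Step 1: units.** Let time be coded in units of u days.

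- Correct rate = (slope/baseline) × (365/u) × 100
- SAP rate = (slope/baseline) × (365/T) × 100
- SAP rate / correct rate = u/T, which equals 1 only when u = T.

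**Step 2: reported rate when the truth is -2.00**

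| Treated to | T | 365/T | Time in years | Time in weeks | Time in days | Time as day/T |
|---|---|---|---|---|---|---|
| Week 48 | 335 | 1.090 | -2.18 | -0.0418 | -0.0060 | -2.00 |
| Week 96 | 671 | 0.544 | -1.09 | -0.0209 | -0.0030 | -2.00 |
| Week 144 | 1007 | 0.362 | -0.72 | -0.0139 | -0.0020 | -2.00 |
| Week 216 | 1511 | 0.242 | -0.48 | -0.0093 | -0.0013 | -2.00 |

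With time in years the value is 9% too large at T = 335 and falls below the truth once T exceeds 365. The ratio between any two rows is the same for every fixed unit.

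**Step 3: analysis (1).** With equal true slopes, the delayed group's reported rate divided by the early group's is T(early)/T(delayed).

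| Data to | Early T | Delayed T, Week 48 entry | Ratio | Delayed T, Week 24 entry | Ratio |
|---|---|---|---|---|---|
| Week 96 | 671 | 335 | 2.00 | 503 | 1.33 |
| Week 144 | 1007 | 671 | 1.50 | 839 | 1.20 |
| Week 216 | 1511 | 1175 | 1.29 | 1343 | 1.13 |

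**Step 4: analysis (3) against analysis (2).** In (2), T = 335. The reported ratio is 335/T(3), and the false slowing is 1 minus that.

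| Data to | T(3), OLE time only | False slowing | T(3), all study-drug time | False slowing |
|---|---|---|---|---|
| Week 96 | 335 | 1 − 335/335 = 0% | 671 | 1 − 335/671 = 50% |
| Week 144 | 671 | 1 − 335/671 = 50% | 1007 | 1 − 335/1007 = 67% |
| Week 216 | 1175 | 1 − 335/1175 = 71% | 1511 | 1 − 335/1511 = 78% |

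**Step 5: later data cut, same efficacy data.** If efficacy data end at Week 96 but T runs to Week 144, the reported rate is 671/1007 = 0.67 of the Week 96 value, with no new measurement.

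**Step 6: planned difference in % change/year.** With time in years, a true difference of 1.0 point per year is reported as 1.09 at T = 335, 0.54 at T = 671 and 0.36 at T = 1007.

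**Step 7: numerical check.** A random intercept and slope model was fitted to one simulated data set of 34 subjects at each of three values of T.

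| T | Correct rate from the fit | SAP formula, time in years | SAP formula, time as day/T |
|---|---|---|---|
| 335 | -1.856 | -2.022 | -1.856 |
| 671 | -2.211 | -1.203 | -2.211 |
| 1007 | -2.031 | -0.736 | -2.031 |

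The SAP formula agrees with the correct rate only under day/T coding.

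**The case against.** The best defence is that this is an omission rather than an error. A 365/T factor, with the minus 1 that undoes the plus 1 of Section 7.2.1, is what an author would write if slope meant change over T. Study day and the visit table are not named as the model covariate. Section 4 places the table shells in a separate document, which may state the unit. Coding in days or weeks would give values so small (-0.0060 or -0.0418) that quality control would probably catch them.

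Some of this stands:

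- The finding is conditional on coding, and day/T coding removes the scale error.
- A plausible-looking wrong number mainly requires time in years.
- Counting placebo-controlled weeks in T for (3) is the less natural reading, since (3) uses OLE data.
- Week 216 is an extreme case for efficacy data. Protocol version 5.0 is dated 16 August 2022, and 1512 days earlier is June 2018, whereas the protocol number carries 2019. It matters chiefly if T runs to last dose; SAP 7.2.1 and Table 4-1 do provide for 216 weeks.
- Analysis (1) has no planned between-sequence test, and the aim of (2) and (3) is exploratory.

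The defence does not rescue the text. The ratios across T are the same for every fixed unit, and the only time scales the SAP defines are fixed. Day/T coding would still need a defined T, so the wording has to change under either reading.

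**Conclusion.** The formula is wrong as written. It gives a correct annual rate only under day/T coding, which the SAP nowhere states. With any fixed unit every % change/year is mis-scaled by u/T. On OLE-only T, the comparison of (3) with (2) shows no false slowing at Week 96 and 50% at Week 144; more generally there is false slowing whenever T in (3) exceeds about 335 days. In (1), Week 48 entrants starting late appear to change 2.0 times as fast as early starters at Week 96 and 1.5 times as fast at Week 144. These figures assume equal true slopes and T set by the visit schedule.

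The reach is limited. Model slopes, the slope difference with its interval and p-value, and by-visit summaries are unaffected. Within (2), and within (3) when durations are similar, the ratio between sequences is preserved, though the level and the difference are not. The affected outputs are secondary (MRI) and exploratory OLE summaries; the OLE primary safety endpoint is not involved. This should be fixed before the annualized tables are produced.

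**What to change.** In SAP Section 8.1, state one time unit for all three models, annualize by that unit alone, and remove T:

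- Time in days: % change/year = 100 × slope × 365 / LS-mean intercept.
- Time in years: % change/year = 100 × slope / LS-mean intercept.

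Carry the same text to individual muscles, reachable workspace, classic TUG and dynamometry.

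If time was meant as day/T, say so and define T: subject, group or nominal; its start date in (3); and whether it ends at the last efficacy assessment or the last dose.

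A delta-method or bootstrap interval for the annualized rate would be a useful but optional addition. The cost is SAP wording and a small programming change, with no new data.

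### SAP 8.1 slope models name time and sequence-by-time only as random effects, so the promised mean slopes, slope difference, CI and p-value are not contrasts of the model as stated

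*SAP*

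**What the plan says.** SAP 8.1 defines three annualised-change analyses of the MRI longitudinal composite scores.

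- Analysis (1) uses all data on losmapimod and is fitted separately for each treatment sequence, "with intercept and time as random effects, and with adjustment for repeat number category and region".
- Analysis (2) uses the placebo-controlled period for subjects who completed 48 weeks of it, "with treatment sequence as a fixed effect, and intercept, time and treatment sequence-by-time interaction as random effects", adjusting for repeat category and region.
- Analysis (3) covers the OLE: "The same approach as in (2) will be used to analyze the longitudinal composite scores in the OLE".

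From (2), and so from (3), the SAP promises slopes and intercepts by sequence with standard errors, and the "difference in the LS mean of slope and the associated 2-sided 95% CI and 2-sided p-value will be derived from the linear mixed-effects model". In all three analyses, % change/year divides the slope by the LS mean of the intercept.

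On covariance, 8.1 says: "An unstructured covariance matrix will be used to model the correlations between repeated measurements within each subject". The fallbacks are that "if any model using an unstructured covariance matrix does not converge, an AR(1) covariance structure will be used" and, if that also fails, "a compound symmetric covariance structure will be used instead".

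Sections 8.2.1 (RWS), 8.2.2 (classic TUG) and 8.2.3 (dynamometry) adopt similar approaches. The table list in SAP 14.4 contains 27 annualised-change tables: 6 each for MFF, LMV and MFI, and 3 each for RWS, classic TUG and dynamometry. Eighteen of them are for the placebo-controlled or OLE period alone, that is, types (2) and (3).

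**The concern.** The sentence in (2) sorts its own terms into fixed and random, and it puts everything that involves time on the random side. An LS mean, or a difference of LS means, is a contrast of fixed effects. If no fixed term contains time, there is no parameter for a mean slope, and none for a difference between sequences to which a CI or p-value could attach. No other passage in the SAP supplies a fixed time term for these models, and the convergence fallbacks change only the covariance.

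An analyst who follows the text literally must either depart from it or report something else, such as averaged predicted slopes, which shrink toward zero. These slope differences are the only between-sequence p-values that this SAP describes. They feed its stated purpose "to explore the possibility that earlier treatment with losmapimod is better than delayed treatment".

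**Working it through.** No figure in the plan bears on this, so the check is one of estimability.

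**Mean model.** Inputs from SAP 8.1: two sequences in (2) and (3), two repeat categories, three regions. Counting an overall mean, the fixed columns are 1 (mean) + 1 (sequence) + 1 (repeat category) + 2 (region) = 5. As written, because the random terms have mean zero,

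E[y] = μ + sequence + repeat category + region.

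The expected change between any two visits is 0 in each sequence, so the slope difference is 0 by construction. The % change/year numerator is likewise 0. With time and sequence-by-time fixed,

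E[y] = μ + sequence + repeat category + region + (β + δ × sequence) × time,

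which has 5 + 2 = 7 columns. A numerical check gave rank 5 for the first design, with time outside its span, and rank 7 for the second. The slopes are then β and β + δ, and the difference is δ. For (1), fitted by sequence, the count is 1 + 1 + 2 = 4 columns without time and 5 with it. None of this depends on assumed variances.

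**Covariance.** Take a random intercept and slope (3 parameters: two variances and a covariance) plus a residual matrix. Three visits give 3 × 4 / 2 = 6 distinct variances and covariances; four give 4 × 5 / 2 = 10. The ranks below are those of the marginal covariance as a function of its parameters.

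| Residual matrix | Weeks 0/12/48 or 48/72/96: parameters, rank | Weeks 48/72/96/120: parameters, rank |
|---|---|---|
| Unstructured | 3 + 6 = 9, rank 6 | 3 + 10 = 13, rank 10 |
| AR(1) | 3 + 2 = 5, rank 5 | 5, rank 5 |
| Compound symmetry | 3 + 2 = 5, rank 4 | 5, rank 4 |

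The visit sets follow the MRI schedules in Protocol 3.1.1 and SAP 14.2. Compound symmetry loses one rank because its common covariance and the random-intercept variance enter only as a sum. If the unstructured matrix is instead that of the random effects, the AR(1) and compound-symmetry fallbacks would force intercept and slope to share one variance, although their units differ.

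**Illustration only.** The documents give no variances or slopes for these scores, so all values here are assumed. Both exercises used 34 subjects per sequence, from 80 enrolled − 12 Week 24 rollovers = 68 at most (Protocol 3.1.1), with an equal split assumed. The quantity examined was the difference in averaged predicted random slopes under the literal model.

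- *Scans at Weeks 0/12/24/48, intercept SD 1, true difference 0.30 per year.* The literal difference was 0.177 (0.177/0.30 = 59%) at slope SD 0.2 and residual SD 0.2. It was 0.075 (25%) at 0.2 and 0.4, and 0.060 (20%) at 0.1 and 0.4. With fixed time terms it was 0.296, 0.290 and 0.294. With equal true slopes, the fixed-term test rejected 5.3% of the time at nominal 5%.
- *Scans at Weeks 0/12/48, intercept SD 3, residual SD 1, slope SD 0.5 to 4.* The literal difference was 25% to 79% of a true 0.5 per year, and 55% to 85% of a true 1.0. The fixed-term means were within one Monte Carlo standard error of the truth.

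**The case against.** The best defence is that this is shorthand. Calling a coefficient random need not deny it a population mean, and 8.1 itself takes an LS mean of an intercept that it lists only as random. Together with the promised slope SEs, CI and p-value, that points to an ordinary random-coefficients model with non-zero mean slopes. The table shells (SAP 4) and the separate placebo-period SAP (SAP 1) are not among the documents and may state the terms correctly. This largely stands as to intent. It does not repair the text, which explicitly separates fixed from random. Protocol 7.6.3, for its categorical-visit repeated-measures model, does list visit and treatment-by-visit as fixed; that is a different model, but it shows the distinction is drawn elsewhere in the plan.

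A reader might infer that the reported slope differences will be biased toward zero. The documents do not support that: the SAP never proposes averaging predicted slopes, and the percentages above rest on assumed variances. Nor do surplus covariance parameters by themselves bias a fixed slope contrast; they are a specification and convergence problem.

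A reader might also infer that the key LMV test at Week 48 is compromised. It is not shown to be. That hierarchy belongs to Protocol 7.6.1, with details left to the placebo-period SAP, and it names FSHD TUG, whereas the slope analysis in 8.2.2 covers classic TUG.

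**Conclusion.** The specification is wrong as written and should be corrected. In (2) and (3) the stated model has no parameter for the mean slopes, slope difference, CI or p-value that it is said to produce, and in (1) it has none for the slope behind % change/year. This follows from the wording and the column count alone. It establishes an error in the text, not in the analysis that will be run, since the intended model is fairly clear.

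The covariance statement is a secondary fault: under either reading, the unstructured matrix or its fallbacks fit badly with the named random effects.

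The consequence is limited. SAP 3.2.2 lists the MRI scores as secondary OLE endpoints under protocol version 4.0, but 8.1 gives the comparisons in (2) and (3) an exploratory purpose. The reused outcomes are exploratory endpoints in SAP 3.2.3. No primary or alpha-controlled conclusion depends on any of them.

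**What to change.** - In (2) and (3), state time and sequence-by-time as fixed effects alongside sequence, repeat category and region. Define the slope difference as the fixed sequence-by-time contrast.
- In (1), state time as a fixed effect.
- Keep a subject-level random intercept and slope, and say that they are by subject.
- Say which matrix is unstructured, and match the fallbacks to it. Two repairs are acceptable. One makes it the random intercept and slope matrix, with a suitable fallback such as uncorrelated intercept and slope. The other keeps it as the residual matrix with the present fallbacks and drops the random effects. The fixed time terms are needed under both.
- Carry the same wording to 8.2.1, 8.2.2 and 8.2.3, and check the table shells against it.

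The cost is SAP wording and, if the programs followed the text literally, a change to the model statements. Data collection is unaffected.
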